We believe staffing levels are sufficient given the total recruitment target of 10 individuals with SCI and the tasks to be accomplished during the two-year study.

e) Access to target population.

Explain and justify whether you will have access to a population that will allow recruitment of the required number of participants.

We expect to enroll a total of 10 participants with SCI; five individuals in a standard-of-care control group and five individuals in an FES-rowing group. Approximately 35 new patients with SCI are seen per year at the VA Palo Alto Spinal Cord Injury Center. If recruitment from VA Palo Alto proves to be insufficient, we will contact [name] who is the Chief of Spinal Cord Injury, Department of Physical Medicine & Rehabilitation, at the Santa Clara Valley (SCV) Medical Center In San Jose. [name] has agreed to provide consulting assistance as needed on the recruitment of potential participants with spinal cord injuries receiving their medical care at the SCV Medical Center. Approximately 125 new patients with SCI are seen per year at the SCI Rehabilitation Center at SCV Medical Center. Between VAPAHCS and SCV Medical Center, we do not anticipate difficulty in achieving our recruitment target.

f) Access to resources if needed as a consequence of the research.

State whether you have medical or psychological resources available that participants might require as a consequence of the research when applicable. Please describe these resources.

The VA SCI Center provides comprehensive care to patient with SCI on an in- and out-patient basis. There are dedicated physicians, nurses, therapists, and psychologists on staff with extensive experience addressing the medical and mental needs of this patient population. While it is unlikely that there will be research-related events that will require significant medical follow-up, these services are readily available within the facility.

g) Lead Investigator or Coordinating Institution in Multi-site Study.

Please explain (i) your role in coordinating the studies, (ii) procedures for routine communication with other sites, (iii) documentation of routine communications with other sites, (iv) planned management of communication of adverse outcomes, unexpected problems involving risk to participants or others, protocol modifications or interim findings.

1. Purpose

a) In layperson's language state the purpose of the study in 3-5 sentences.

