- resting blood pressure higher than 140/90
- a grade 1 or greater, sacral, gluteal or ischial pressure ulcer
- history of low trauma, lower limb fracture since SCI
- renal disease
- current osteomyelitis
- current thrombosis/hemorrhage
- cancer
- other neurological disease (i.e. stroke, peripheral neuropathy, myopathy)
- any implanted electronic device
- active treatment for epilepsy
- regular use of tobacco
- known coronary artery disease
- family history of sudden cardiac death
- current use of cardioactive medications, e.g., for treatment of congestive heart failure or arrhythmia
- current use of medications that can affect bone density and fracture risk including:
 - bisphosphonates
 - parathyroid hormone (PTH) and PTH analogs
 - androgenic steroids
 - estrogenic steroids
 - glucocorticoids
 - anti-epileptics

We will also exclude patients with cognitive impairments that will limit understanding of the nature of the project or understanding of the informed consent process.

- i) **Describe your screening procedures, including how qualifying laboratory values will be obtained. If you are collecting personal health information prior to enrollment (e.g., telephone screening), please request a waiver of authorization for recruitment (in section 15).**

Subjects initially identified as potential candidates by Drs. [name] and [name] or their clinical colleagues at VA Palo Alto or Santa Clara Valley Medical Center, will be given contact information for [name]. Interested patients will be told to contact [name] to find out about the study and ask any additional questions.

- j) **Describe how you will be cognizant of other protocols in which participants might be enrolled. Please explain if participants will be enrolled in more than one study.**

Title : Skeletal Health in the Lower Limbs Following Spinal Cord Injury
Approval Period: 01/13/2015 - 09/02/2015

Patients will be asked during recruitment if they are participating in any other studies. Participants will not be eligible for our study if they are already participating in another research study that uses drugs or exercise to maintain skeletal health.

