- a) For the following categories include a scientific estimate of the frequency, severity, and reversibility of potential risks. Wherever possible, include statistical incidence of complications and the mortality rate of proposed procedures. Where there has been insufficient time to accumulate significant data on risk, a statement to this effect should be included. (In describing these risks in the consent form to the participant it is helpful to use comparisons which are meaningful to persons unfamiliar with medical terminology.)

The risks of the Investigational devices.

This study will use an Odstock 4-channel muscle stimulator (model O4CHS) that has been used for many years in FES-rowing research studies in England, Canada and the United States. This device is powered by a standard, 9-volt battery identical to those used to power a transistor radio or smoke alarm. Our research consultants in England who are pioneers of FES-rowing programs, and who have helped establish FES-rowing programs in several other research laboratories around the world, have used this exact 4-channel stimulator with approximately 30 subjects with SCI and have never had an adverse event related

Title : Skeletal Health in the Lower Limbs Following Spinal Cord Injury
Approval Period: 01/13/2015 - 09/02/2015

to its use. Researchers at Spaulding Rehab in Boston also have never experienced an adverse event related to the use of the O4CHS device. Given the long history of safe use of the O4CHS device in other FES-rowing programs we believe this device qualifies as a non-significant risk.

The Odstock 4-channel muscle stimulator is used during FES muscle conditioning, FES muscle strength testing, and FES rowing.

The risks of the Investigational drugs. Information about risks can often be found in the Investigator's brochure.

None.

The risks of the Commercially available drugs, reagents or chemicals. Information about risks can often be found in the package insert.

None.

The risks of the Procedures to be performed. Include all investigational, non-investigational and non-invasive procedures (e.g., surgery, blood draws, treadmill tests).

Other than the bone density scans for which the risk is described later, there are no other procedures to be performed on the Standard-of-Care (control) group.

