5) Lower limb fracture during muscle conditioning, strength testing or FES-assisted rowing: The use of FES to stimulate paralyzed muscles in individuals with SCI has been studied for more than 50 years. Over that 50-year period there have been two reported cases of a fracture related to the use of functional electrical stimulation. One individual fractured their patella and a second individual fractured their lateral femoral condyle. Although the total number of individuals with SCI who have used functional electrical stimulation to exercise the lower limbs is not known, we believe the risk of a fracture is very low given that there have only been two reported fractures in 50 years of FES use. To further reduce the risk of fracture, only participants who have never experienced a low-energy or fragility fracture will be allowed to take part in this study. In addition, we will measure bone density for each participant at the beginning of the study and those measurements will provide us with an initial assessment of the health of each participant's femur and tibia. If we believe a participant's bones are too weak to safely undergo the muscle conditioning and rowing exercise, that participant will be withdrawn from the study.

6) Increase in neuropathic pain to an unacceptable level: Some spinal cord injured individuals suffer from neuropathic pain which can range from a mild tickling sensation to a severe burning sensation. It is not known what effect, if any, electrical stimulation has on this condition. In addition, some individuals with SCI who have some sensation in their thighs may find the electrical stimulation to be uncomfortable or even intolerable. Any participant who finds the electrical stimulation to produce neuropathic pain or sensation that is unacceptable to them will be withdrawn from the study.

7) Increase in spasticity to an unmanageable level: It is not known what effect FES has on the intensity and frequency of spasticity. In other FES-rowing programs, a few participants have had an increase in spasticity, while some participants have had a decrease. In general, spasticity levels should be reduced after a muscle conditioning or rowing session, since the muscles will be fatigued. If a subject experiences increased spasticity to a level that is unmanageable, they will be withdrawn from the study.

The risks of the Radioisotopes/radiation-producing machines (e.g., X-rays, CT scans, fluoroscopy) and associated risks.

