Confidentiality of the identifiable information will be carefully protected and data security measures will be strictly enforced. Any information or data on paper, including signed consents, will be stored in locked cabinets in locked offices in a secure VA building. All electronic data that contain identifiable subject information will be saved on a secure VA file server behind the VA firewall. No data will be maintained on portable electronic devices.

Protecting against and minimizing potential risks: To reiterate, the following are the potential risks to participants in the FES-rowing group.

- 1) Soft tissue reaction during FES training
- 2) Muscle strain during muscle conditioning, strength testing or FES-assisted rowing
- 3) Fall during transfer to or from rowing machine
- 4) Serious autonomic dysreflexia (AD) during FES training
- 5) Lower limb fracture during muscle conditioning, strength testing or FES-assisted rowing
- 6) Increase in neuropathic pain to an unacceptable level
- 7) Increase in spasticity to an unmanageable level

The following paragraphs describe how these risks will be mitigated to reduce them to the lowest possible levels.

1) Soft tissue reaction: Other than the typical reddening beneath the electrodes, which is to be expected, we will be vigilant to look for other types of soft tissue reactions and we will encourage all participants to be vigilant. To the best of our knowledge no prior FES-rowing participants have experienced a skin breakdown or pressure sore caused by their participation in an FES-rowing program. Nevertheless, before and after each session, we will look for any signs of bruising or swelling that might be suggestive of tissue breakdown, paying particular attention to the shoulders, back, buttocks, upper calves and knee areas.

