15.1 Waiver of Authorization for pre-screening of potential participants

Recruitment

- a) Describe the protected health information (PHI) needed to conduct screening or recruitment. PHI is health information linked to HIPAA identifiers. List BOTH health information AND HIPAA identifiers. If you are using STARR, use the Data Privacy Attestation to ensure that your request will match your IRB-approved protocol.

Potential participants will typically make their first contact with [name] by phone. During that initial phone call, [name] will provide potential participants with a general overview of the project, including the two possible groups to participate in, the total duration of the study and the time commitment. During that phone call, [name] will also make an initial assessment of potential participants from the perspective of the inclusion and exclusion criteria. This initial assessment is particularly important in terms of convenience to potential participants since all participants will have spinal cord injuries which may make it difficult for them in terms of transportation to and from the VA. The investigators do not want to inconvenience a potential subject by requiring them to come to the VA only to learn after one or two minutes of discussion that the subject is not really interested in the study or does not qualify, say, because of age, or because of the time commitment, or because of one of the inclusion or exclusion criteria. During the initial phone conversation with a potential participant, it is possible that the individual calling will provide his or her name or reveal other III or PHI, such as the city where they live or some health information such as the date or level of their spinal cord injury. It is not possible to have that phone conversation without there being a reasonable likelihood that the individual will reveal some III or PHI. It is not practical or reasonable to require that an individual make a special trip to the VA, sign an informed consent, and only thereafter to determine if they are interested in the study or if they potentially qualify for inclusion.

- b) Please Answer:
 - Y Do you certify that the use or disclosure of protected health information involves no more than a minimal risk to the privacy of individuals?
 - Y Do you certify that the research could not practically be conducted with out the waiver?

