 - Y Do you certify that you have adequate written assurances that the protected health information will not be reused or disclosed to any other person or entity, except as required by law, for authorized oversight of the research project, or for other research for which the use or disclosure of protected health information would be permitted?
 - Y Do you certify that the research could not practically be conducted with out access to and use of the protected health information?
- c) Please describe an adequate plan to protect any identifiers from improper use and disclosure.

During the initial phone call by potential participants to [name] during which the potential participant might disclose PHI or III, [name] will typically take hand-written notes about the potential participant. After the phone conversation, those notes will be transcribed to a WORD document and stored on a secure server at the VA. At that point the handwritten notes will be depositing in a secure bin for shredding. If it is

Title : Skeletal Health in the Lower Limbs Following Spinal Cord Injury
Approval Period: 01/13/2015 - 09/02/2015

subsequently determined that a subject is not a candidate for inclusion or potential inclusion in the study the electronics notes will be permanently deleted from the VA server. Candidates who ultimately do become participants will have any PHI or III appended to their information in the file that contains the code number for participants, which will only be stored on the secure VA server behind the VA firewall.

- d) **Please describe an adequate plan to destroy the identifiers at the earliest opportunity consistent with conduct of the research, unless there is a health or research justification for retaining the identifiers or such retention is otherwise required by law.**

All VA research records will be maintained consistent with existing VA record retention policies.

16. Attachments

Attachment Name	Attached Date	Attached By	Submitted Date
VA Required Questions	08/29/2013	[name]	
VA Consent for use of photos, etc.	08/29/2013	[name]	
VA Proposal	09/26/2013	[name]	
Phone Script	09/29/2013	[name]	

Obligations

The Protocol Director agrees to:

- Adhere to principles of sound scientific research designed to yield valid results
- Conduct the study according to the protocol approved by the IRB

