- Be appropriately qualified to conduct the research and be trained in Human Research protection, ethical principles, regulations, policies and procedures
- Ensure all Stanford research personnel are adequately trained and supervised
- Ensure that the rights and welfare of participants are protected including privacy and confidentiality of data
- Ensure that, when de-identified materials are obtained for research purposes, no attempt will be made to re-identify them.
- Disclose to the appropriate entities any potential conflict of interest
- Report promptly any new information, modification, or unanticipated problems that raise risks to participants or others
- Apply relevant professional standards.

Any change in the research protocol must be submitted to the IRB for review prior to the implementation of such change. Any complications in participants or evidence of increase in the original estimate of risk should be reported at once to the IRB before continuing with the project. Inasmuch as the Institutional Review Board (IRB) includes faculty, staff, legal counsel, public members, and students, protocols should be written in language that can be understood by all Panel members. The investigators must inform the participants of any significant new knowledge obtained during the course of the research.

IRB approval of any project is for a maximum period of one year. For continuing projects and activities, it is the responsibility of the investigator(s) to resubmit the project to the IRB for review and re-approval prior to

Title : Skeletal Health in the Lower Limbs Following Spinal Cord Injury
Approval Period: 01/13/2015 - 09/02/2015

the end of the approval period. A Notice to Renew Protocol is sent to the Protocol Director 7 weeks prior to the expiration date of the protocol.

Department Chair must approve faculty and staff research that is not part of a sponsored project. VA applicants must have Division Chief or Ward Supervisor approval. E-mail the Department Chair approval to [contact].

All data including signed consent form documents must be retained for a minimum of three years past the completion of the research. Additional requirements may be imposed by your funding agency, your department, or other entities. (Policy on Retention of and Access to Research Data, Research Policy Handbook, <http://doresearch.stanford.edu/policies/research-policy-handbook/conduct-research/retention-and-access-research-data>)

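### The risk section bars anyone who has ever had a low-energy fracture, but the section 8(h) exclusion list bars only low-trauma leg fractures since the spinal cord injury

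*Combined protocol and SAP*

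**What the plan says.** Section 9(a), item 5, discusses lower limb fracture during conditioning, strength testing and rowing. Among the measures to lower that risk it states that "only participants who have never experienced a low-energy or fragility fracture will be allowed to take part in this study". Section 9(c), item 5, repeats the sentence. It sets no limit on time or on skeletal site.

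Section 8(h) gives one exclusion list for both groups. Its only entry on fracture history is "history of low trauma, lower limb fracture since SCI". Fracture is mentioned once more in that list, in the entry on medications that affect bone, which is not a fracture-history criterion.

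Under section 15.1, the first phone call with a candidate is used to "make an initial assessment of potential participants from the perspective of the inclusion and exclusion criteria".

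**The concern.** The plan holds two different rules on who may enter. The stricter one appears only in the risk text, and the list that screening staff would consult holds the looser one. The stricter rule is offered to the IRB as protection for people whose paralysed legs will be electrically stimulated. If screening follows 8(h) as written, that protection is not applied to someone whose fracture came before the injury.

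What is at stake is one layer of safety screening and the accuracy of what the IRB was told. Bone-density outcomes and their summary do not depend on it.

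**Working it through.** The plan gives no figure on this point, so there is nothing to reproduce and no arithmetic applies. The check is a comparison of the texts, taking low-trauma and low-energy to mean the same thing.

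1. **Time.** Item 5 covers a person's whole life. The 8(h) criterion starts at the SCI. Entry is 3 to 12 months after injury (8(h)), so the criterion looks back 12 months at most. The stated age range is 18 to 50 years (8(b)), so most of each candidate's life lies outside that window.

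2. **Site.** Item 5 names no site in the sentence itself, while 8(h) names the lower limb. Because item 5 is headed as a lower limb risk, the sentence may be meant for leg fractures only.

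3. **Both readings of item 5 against 8(h):**

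| Earlier low-energy fracture | 8(h) list | Item 5, any site | Item 5, leg only |
|---|---|---|---|
| Leg, since SCI | barred | barred | barred |
| Leg, before SCI | **not barred** | barred | barred |
| Other site, since SCI | not barred | barred | not barred |
| Other site, before SCI | not barred | barred | not barred |

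The second row decides the matter: the texts disagree there on either reading. The last two rows disagree only if item 5 is read literally. The rows are not equally common or equally hazardous, so they should not be counted up as a share of risk. The row that 8(h) does cover is the one closest to the post-injury bone loss that motivates the study.

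4. **Could another provision close the gap?** For rowers, 8(h) asks for a physician's clearance to exercise, which is not a fracture-history rule. Item 5 provides for withdrawal if the baseline scans suggest the bones are too weak, and section 9(d) lists markedly low bone density as a reason for withdrawal. Both are judgements without a stated threshold, made after a study scan. Item 5 of 9(c) adds teaching on the signs of fracture. The skin inspection around each session (9(c), item 1) is directed at soft-tissue breakdown and does not count as a fracture precaution. None of these applies the rule that item 5 announces.

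**The case against.** The strongest reply is that no one need be wrongly enrolled. Both rules sit in the same application and are compatible, since anyone who applies the stricter one satisfies both. The Protocol Director undertakes to "Conduct the study according to the protocol approved by the IRB", and the training section says that staff will read the IRB protocol, which contains 9(a) and 9(c). The phone call is described as an initial assessment and not as the only check. The phone script is listed as an attachment but is not reproduced, so it may already ask about earlier fractures. All of this stands. A reader might infer that the safeguard will in fact fail, and the documents do not support that. They show that enforcing it depends on staff taking an eligibility rule from two risk paragraphs when the eligibility list says something narrower.

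A second reply is that few candidates will be affected. The age range is 18 to 50, and post-menopausal women, people with renal disease or cancer, and current users of several bone-active drugs are excluded. That is reasonable and supports calling the gap small. It does not reconcile the texts.

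A third is that the hazard concerns rowers alone. Section 9(c) introduces the list with "the following are the potential risks to participants in the FES-rowing group", and 9(a) says that, apart from the scans, "there are no other procedures to be performed on the Standard-of-Care (control) group". The safety argument indeed does not reach controls. Item 5 nevertheless speaks of taking part in the study. A rule for rowers only would also introduce a difference in fracture history between the groups of a bone-density study. Section 2(a) wants the groups matched, where possible, on age, gender and time since injury. It does not name fracture history, but a new difference of this kind would work against comparability for no real saving.

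**Conclusion.** The inconsistency is real and worth correcting, and it is small. Item 5 bars a person with a low-energy leg fracture before the SCI, and the 8(h) list does not. This conclusion rests only on the wording and on treating low-trauma and low-energy as equivalent.

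Two stronger statements should be avoided. First, a reader might put a probability on enrolling someone whom item 5 bars. The documents give no prevalence of earlier fractures, so any such figure would only restate the value assumed. Such a figure would not be a fracture risk in any case. Second, a reader might take the planned "five individuals in an FES-rowing group" as a ceiling on the number exposed. Section 2(g) keeps the study open until five have completed the programme, so more than five may start, and section 2(a) adds an experienced rower for part of the measurements.

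The baseline density check remains in place, and there is no consequence for the endpoint or the analysis.

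**What to change.** In section 8(h), for both groups, replace the present fracture entry with: *any previous low-energy or fragility fracture, before or since SCI*. Ask about it in the existing phone screen, if the script does not already do so.

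This literal version also excludes people whose only fracture was outside the leg, for whom the link to the hazard in paralysed legs is less direct. If the investigators mean leg fractures only, 8(h) should read: *any previous low-energy lower limb fracture, before or since SCI*. Item 5 should then be reworded to match in both 9(a) and 9(c).

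The cost is an IRB amendment, because "Any change in the research protocol must be submitted to the IRB for review prior to the implementation of such change", and at most one added phone question. No visit, scan or radiation dose is added. A few candidates may be lost, and the documents do not allow their number to be estimated.
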